9.6 Subgroups

The analyses described in this section will be conducted on the ITT set.

Descriptive statistics of eGFR values and the change from Baseline will be summarized by visit and treatment arm for all subgroups defined in Section 7.4.

The statistical approach used for the primary analysis (Section 9.2) will be repeated for all these sub-groups.

For each of the subgroups, the primary model (i.e., two-stage with quantile regression) will be used for each level of the subgroup separately with the same covariates as the primary model. A 95% CI for the treatment effect within each level of a subgroup will be presented.

The results will be presented graphically by a forest plot.

10. ANALYSIS OF SECONDARY EFFICACY ENDPOINTS

All the analyses of secondary end-points will be performed on the ITT set.

10.1 Analysis of Fabry Kidney Disease Therapeutic Goals

Patients will be classified into three kidney disease (KD) groups, based on their eGFR slope at baseline. The therapeutic goals (See Wanner et al., 2018) will be evaluated for each of the categories.

KD Group	Criteria	Therapeutic Goals
Stable KD	Slope at baseline \geq -3 mL/min/1.73 m ² /year	post-treatment slope ≥ -3 mL/min/1.73 m²/year
Progressing KD	Slope at baseline \geq -5 and \leq - 3 mL/min/1.73 m ² /year	post-treatment slope ≥ -3 mL/min/1.73 m²/year
Fast-progressing KD	Slope at baseline< -5 mL/min/1.73 m ² /year	post-treatment slope ≥ -5 mL/min/1.73m²/year, OR > 50% decrease in progression (i.e., (eGFR slope at baseline – post-treatment eGFR slope) / eGFR slope at baseline > 50%)

Table 2: Therapeutic Goals

The individual slopes calculated in the 1st stage described in Section 9.2 will be used for the analyses described in this section.

The number and percentage of patients achieving therapeutic goals (yes/no) will be presented overall and for the three KD groups by treatment arm. A 95% Clopper Pearson CI for the difference in the percentages between the two treatment groups will be presented. The analysis will be repeated for sub-groups: gender, Fabry disease status, ADA status and UPCR category at Baseline.

A shift table between the three categories from Baseline to post-treatment will be presented by treatment arm.

The analysis will be repeated for the Per-Protocol set.

10.2 Plasma Lyso-Gb3 Concentrations

Descriptive statistics of plasma Lyso-Gb3 concentration (nM) will be summarized at each visit. The change and percent change from Baseline will be summarized as well.

A MMRM approach will be used to model the change from baseline of log of plasma Lyso-Gb3. The outcome will consist of the change from baseline of log of Lyso-Gb3 at each post baseline visit. The variables to be included in the model are log plasma Lyso-Gb3 at Baseline, visit (class variable), treatment (class variable), visit by treatment interaction term.

The first choice for the within-patient correlations will be an unstructured covariance structure. If the model does not converge, the model will be fitted assuming a heterogeneous Toeplitz structure, followed by a homogeneous Toeplitz structure, and then a compound symmetry structure until a stable model is achieved. Only data at scheduled visits will be used for this analysis. Missing data will not be imputed. The Kenward-Roger degrees of freedom approximation will be used. Appendix A.2 (Section 17) provides details and pseudo-SAS code for this analysis.

95% CI for the contrast between treatment arms at 1-year visit (Week 52) and at the 2-year visit (Week 104) will be presented, as well as the two-sided p-value for the null hypothesis of no difference between the two arms. Adjusted LSMEANS of the two treatment arms for the change from Baseline to 1-year and from Baseline to 2-year will be presented along with a 95% CI.

The analysis will be repeated for the following subgroups: ADA status, gender and FD classification. A 95% CI for the treatment effect within each level of a subgroup will be presented.

The mean \pm SE of plasma Lyso-Gb3 and the change from baseline over time will be presented graphically by treatment group and by gender.

The number and percentage of patients who improved by at least 30%, 40% and 50% will be summarized at Week 52 and at Week 104 by treatment arm and for the above sub-groups.

10.3 Plasma Gb3 and Urine Lyso-Gb3 Concentrations

Descriptive statistics of plasma Gb3 concentration (nM), and urine Lyso-Gb3 concentration (pM/mM Creatinine) will be summarized at each visit by treatment group. The change and percent change from Baseline will be summarized as well. A 95% CI for the difference between the two arms will be presented for the change from baseline and percent change from baseline using t-distribution for 2-samples.

The analysis will be repeated by gender and by ADA status.

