10.3.2 Secondary Efficacy Analyses

Additional secondary endpoint analyses will be detailed in the final Statistical Analysis Plan

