10.6 Missing Data

The primary analysis will use a mixed models approach for comparing groups. This approach handles missing data appropriately if the missing data is considered to be missing at random (MAR). This would be the expectation. Therefore, all patients should be able to provide at least some data for the primary efficacy comparisons.

For secondary efficacy analyses, since measures are being measured at multiple time points, mixed models will be used and therefore missing data will be handled by the analytic method if the missing data is MAR.

No imputation will be made for missing values of safety endpoints except for some AE parameters as described above.

Episodes of Acute Kidney Injury (AKI) will be considered missing data for the purposes of the primary efficacy analysis. AKI will be defined by a 1.5 fold increase in serum creatinine from the immediately previous laboratory value and assessment by the investigator. However, prior to data base lock and unblinding, cases of AKI will be assessed by two independent nephrology experts. Their evaluation will include whether they agree that AKI occurred in a patient and whether serum creatinine values should be excluded from the eGFR slope calculations for the primary endpoint. Excluded serum creatinine values will be considered missing data.

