1. INTRODUCTION

This statistical analysis plan (SAP) contains detailed information on the definition of the analysis populations, derivation of variables, conventions of analysis scope, and statistical methodology for the analyses of efficacy and safety of pegunigalsidase alfa (also known as PRX-102) and agalsidase beta administered by intravenous (IV) infusion based on data collected per protocol PB-102-F20, a Phase 3 study sponsored by Protalix Ltd. Should the SAP and the protocol be inconsistent with respect to the planned analyses, the language of the SAP is governing.

The pharmacokinetic (PK) analysis is not within the scope of this SAP and is detailed in a standalone PK analysis plan.

A pre-planned interim analysis occurred when the last patient completed the 12-month visit to support a Marketing Authorization Application (MAA) submission to the European Medicines Agency (EMA). The final analysis will occur when the last patient completes the 24-month visit and will support a biologics license application (BLA) re-submission to the FDA.

The SAP that was signed on April 15th, 2021 prior to Data Base Lock (DBL) and unblinding for the interim analysis, included non-inferiority of PRX-102 compared to agalsidase beta for the interim analysis and superiority of PRX-102 compared to agalsidase beta for the final analysis. However, following the conversion of agalsidase beta to a full approval in March 2021, it was agreed with the FDA (End-of-Review Meeting, Sep 9th, 2021) that it is not necessary anymore to demonstrate superiority over agalsidase beta. A Type C meeting to reach agreement with the FDA on the proposed primary model to assess non-inferiority took place in January 21, 2022 and the SAP reflects this discussion.

In addition, analysis that were conducted as post-hoc after the interim analysis are added to the SAP, as well as some other minor changes (all are documented). None of the analyses performed at the interim analysis will be removed but following a comment by FDA, covariates were changed.

As this SAP is now only for the final analysis, sections/paragraphs relating to the interim analysis were deleted and/or updated to include only the final analysis.

In light of the unplanned conversion of agalsidase beta to a full approval and the change in regulatory requirements following that, some changes had to be made also to the unblinding plan.

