2.2.2 Secondary Efficacy Endpoints

The secondary efficacy endpoints are as follows:

- Change from baseline to all time points in the following measures:
 - Plasma globotriaosylsphingosine (Lyso-Gb3)
 - Left Ventricular Mass Index (LVMI) (g/m²) by Magnetic Resonance Imaging (MRI)
 - Plasma globotriaosylceramide (Gb3)
 - Urine Lyso-Gb3
 - Protein/Creatinine ratio spot urine test
 - Frequency of pain medication use
 - Exercise tolerance (Stress Test)
 - Short Form Brief Pain Inventory (BPI)
 - Mainz Severity Score Index (MSSI)
 - Quality of life (EQ-5D-5L)
- Fabry Clinical Events (FCE)
- Achieving Fabry Kidney Disease therapeutic goals

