13. CHANGES IN PLANNED ANALYSIS

13.1 Changes from Protocol to Interim Analysis SAP

The statistical section of the protocol is short and was not meant to provide detailed information for the analysis. Some of the changes in the planned analysis of PB-102-F20 are due to knowledge and insights gained in the overall clinical program of PRX-102. The analysis of the primary endpoint and its associated sensitivity analyses were discussed and agreed by the FDA. The main changes in the analysis plan compared to protocol are as follows:

- 1. The following endpoints were added: Infusion Related Reaction (IRR), Fabry Clinical Events and Achievement of Fabry Kidney Disease Therapeutic Goals.
- 2. Analysis sets: the protocol defined that a patient who received at least one complete dose will be included in the ITT and the SAP changed this to also include at least one partial dose. The definition of the Per Protocol population was also slightly revised.
- 3. The primary analysis was discussed with the FDA after protocol was finalized, and the agreement is described in the SAP. In particular added clarity on the choice of mixed model used, method of estimation and covariance matrix. UPCR which is a stratification factor was added as a covariate which is in line with ICH-E9. The discussion with the FDA included sensitivity for missing data and for modeling assumptions, which is different from what was described in the protocol.
- 4. The protocol specified assessment of the linearity assumption via residual plots. This was changed and instead it will be assessed by the MMRM model on the change in eGFR which does not assume linearity. In case of disagreement, additional assessments will be performed post-hoc.
- 5. The approach for multiplicity control was changed from the protocol, and was discussed and agreed with the FDA.
- 6. The only shift table for laboratory value will be for ADA. No other shift tables will be performed as no other safety laboratory values are of special interest.
- 7. Evaluation of Acute Kidney Injury is based on AE reporting and clinical judgment of the investigator and not as described in the protocol.
- 8. The statistical section of the protocol stated that hypersensitivity will be analyzed as an AE of special interest. Since IRR is a wider analysis which was added (see item 1 in this list), the analysis of hypersensitivity will be part of the IRR evaluation.

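### SAP 10.3 compares plasma Gb3 and urine lyso-Gb3 only by unadjusted t-intervals on raw and percent change, an unrecorded and less precise choice than the log-scale MMRM already planned for plasma lyso-Gb3

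*SAP*

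**What the plan says.** Plasma Gb3 and urine lyso-Gb3 are listed secondary endpoints in SAP 2.2.2, under "Change from baseline to all time points in the following measures".

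- **SAP 10.3** gives both markers descriptive statistics by visit and then a two-sample interval: "A 95% CI for the difference between the two arms will be presented for the change from baseline and percent change from baseline using t-distribution". It names no visit for the interval. The analysis is repeated by gender and by ADA status.
- **SAP 10.2** treats plasma lyso-Gb3 differently: "A MMRM approach will be used to model the change from baseline of log of plasma Lyso-Gb3". Log baseline, visit, treatment and visit by treatment are the model terms, and contrasts are given at Week 52 and Week 104.
- **Protocol 10.6** says of secondary efficacy analyses: "since measures are being measured at multiple time points, mixed models will be used". The reason given is that missing data are then handled under MAR.
- **Protocol 10.3.2** leaves room for the SAP: "Additional secondary endpoint analyses will be detailed in the final Statistical Analysis Plan".
- **SAP section 1** sets precedence: "Should the SAP and the protocol be inconsistent with respect to the planned analyses, the language of the SAP is governing".
- **SAP 13.1** introduces its list with: "The main changes in the analysis plan compared to protocol are as follows". Neither its eight items nor the nineteen items of 13.2 mention a move away from mixed models for these two markers.

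**The concern.** The flow charts schedule all three substrate markers at the same visits (1, 4, 7, 14, 20, 27, 40 and 53). One gets a longitudinal, baseline-adjusted comparison on the log scale. The other two get comparisons that do not adjust for baseline and that use only patients observed at the visit in question. The SAP gives no reason for the difference.

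Precision is what is at stake. If concentrations are right-skewed, the mean raw change is driven by the few patients with high baseline values. In a trial randomised 52:26, chance baseline imbalance stays in an unadjusted change score. A reader who sets the three markers side by side would see an adjusted log contrast for one and unadjusted differences for the other two, with nothing in the SAP to explain why.

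**Working it through.** **Text comparison.** SAP 10.3 contains none of the three features that SAP 10.2 has (log scale, baseline term, repeated-measures model). It also departs from the general method in protocol 10.6. SAP 13.2 item 3 lists the models from which UPCR was removed, and lyso-Gb3 is the only biomarker among them.

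**No plan figure to reproduce.** The documents give no sample size, power, SD or correlation for either marker. Everything below therefore rests on assumed inputs.

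**Step 1: gain from baseline adjustment alone.** Assume equal SD σ at baseline and follow-up, with correlation ρ between them.

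- Variance of change: 2σ²(1 − ρ)
- Residual variance after baseline adjustment: σ²(1 − ρ²)
- Ratio of variances: (1 + ρ)/2, so the ratio of interval widths is √((1 + ρ)/2)

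| ρ | Adjusted width / unadjusted width |
|---|---|
| 0.3 | √0.65 = 0.81 |
| 0.5 | √0.75 = 0.87 |
| 0.7 | √0.85 = 0.92 |
| 0.8 | √0.90 = 0.95 |
| 0.9 | √0.95 = 0.97 |

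Inverting the ends, the unadjusted interval is about 3% wider at ρ = 0.9 (1/0.975) and 24% wider at ρ = 0.3 (1/0.806). A chance imbalance of 0.3 SD at baseline moves the unadjusted difference in change by (1 − ρ) × 0.3 SD in the opposite direction. That is 0.15 SD at ρ = 0.5, 0.09 SD at 0.7 and 0.03 SD at 0.9.

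**Step 2: gain from the log scale as well, with 44:22 completers (SAP 3.1).** Log-normal data, true 25% reduction on PRX-102, 4,000 simulated trials per row. Entries are the share of trials in which the 95% interval excludes no difference.

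| Log SD, ρ | Raw change | Percent change | Log change, log-baseline adjusted | Raw loss (points) | Percent loss (points) |
|---|---|---|---|---|---|
| 0.5, 0.8 | 0.80 | 0.92 | 0.95 | 15 | 3 |
| 1.0, 0.9 | 0.33 | 0.66 | 0.69 | 36 | 3 |
| 1.0, 0.95 | 0.54 | 0.92 | 0.93 | 39 | 1 |

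**Step 3: a second set of assumptions, with 52:26 randomised.** True 20% lower level on PRX-102, within-patient log SD 0.2, log-change SD 0.2-0.3, baseline log SD 0.5-0.8.

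- Half the patients female, at one fifth of the male level: raw change 29-47%, adjusted log change 59-76%.
- No sex difference: raw change 38-62%, adjusted log change 62-76%.
- Percent change loses about 0-3 points against adjusted log change in these settings.
- Baseline log SD of only 0.2-0.3 and no sex difference: raw change loses about 10 points and percent change up to about 7.

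**Step 4: validity.** With no true difference, all three methods reject in about 4-5% of simulated trials.

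These simulations compare methods at one visit with complete data. They do not measure any gain from modelling the visits jointly or from handling missing draws.

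**The case against.** The case for leaving 10.3 alone has real substance.

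- **The SAP is the operative text.** It governs over the protocol, the protocol defers secondary detail to it, and 13.1 claims to list only main changes. A reader might infer that protocol 10.6 must override 10.3. The documents do not support that. What remains is an unrecorded departure and an unexplained inconsistency.
- **Percent change is already planned.** It recovers most of the lost precision, so the large losses apply only to the raw-change interval. This stands.
- **Skew is not documented.** A reader might take the protocol's introduction, which describes marked elevation in males and raised levels in symptomatic females, as evidence for these markers. That text is about lyso-Gb3, and the male statement is about plasma. It does not describe plasma Gb3 or urine lyso-Gb3 in patients with at least a year of agalsidase beta behind them. SAP 10.3 also already repeats its analysis by gender.
- **The markers can still be read together descriptively.** A reader might infer that they cannot. SAP 10.2 also summarises change and percent change for plasma lyso-Gb3, so only the between-arm inference differs.
- **Missing data.** A reader might infer a material loss. SAP 16.2 reports 6 of 78 patients (7.7%) discontinued, and SAP section 6 says home care covered blood sampling for biomarkers. It does not mention urine, so the reassurance is firmer for plasma Gb3.
- **Nothing confirmatory depends on it.** SAP 7.6.2 makes secondary results nominal only.
- **Other endpoints follow the same pattern.** LVMI, BPI, MSSI and the EQ-5D-5L health score also get two-sample t comparisons. The case is stronger for these two markers because a model for a closely related marker, drawn on the same schedule, is already specified.

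**Conclusion.** The point holds as one of precision and documentation. SAP 10.3 plans only unadjusted t-intervals for two of the three substrate markers, protocol 10.6 points to mixed models, SAP 10.2 already contains a suitable one, and section 13 does not mention the difference.

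The intervals are valid, and it would be wrong to call them biased. If the markers are skewed, raw change gives up roughly 10 to 40 points of power against log change adjusted for log baseline, depending on the assumed spread, correlation and sex mix. Percent change gives up about 0-3 points in most of the settings tried and up to about 7 with small baseline spread. The direction was the same in every setting with a true difference. The size cannot be fixed from the documents. Trial success and the type I error of the primary analysis are unaffected.

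**What to change.** 1. In SAP 10.3, add the 10.2 model for plasma Gb3 and for urine lyso-Gb3: an MMRM on change in log concentration with log baseline, visit, treatment and visit by treatment. Report the Week 52 and Week 104 contrasts back-transformed to ratios, and name this the lead between-arm comparison.
2. Keep the raw and percent-change intervals. SAP section 1 and 16.3.1 say that analyses performed at the interim will not be removed, and 13.2 lists no change to 10.3, so these intervals were presumably among them.
3. Correct SAP 17.7 before reusing it. Its MODEL statement has the baseline variable logLysoGb3BL as the response, and also as a covariate, whereas the text defines the response as logLysoGB3_CH. Its closing note sets only the Week 104 contrast for the final analysis, so Week 52 must be added.
4. Record the addition in section 13.2, with the reason.

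The cost is SAP wording and two more model runs, with lead results expressed as ratios and not in concentration units. The change would also come late: under 16.3.1 the SAP is updated by the unblinded statistician after the interim results. It must therefore be documented as a post-interim addition made for consistency with 10.2 and protocol 10.6.

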10.4 Cardiac Assessments

10.4.1 Cardiac MRI

Left ventricular mass (LVM), left ventricular mass index (LVMI, indexed to patient's body surface area (g/m²)), and left ventricular ejection fraction (%EF) will be summarized using descriptive statistics for each visit that includes these evaluations. The change from baseline will be summarized. A 95% CI for the difference between the two in the change from baseline to Week 52 and to Week 104 arms will be presented using t-distribution for 2-samples. The LVM and LVMI analysis will be done separately for patients who have hypertrophy at baseline, patients who don't have this abnormality, and patients whose hypertrophy at baseline is missing. Hypertrophy is defined as LVMI above 91 g/m² for males and LVMI above 77 g/m² for female (Kawel-Boehm (2015)).

In case that LVM at a visit is available, and LVMi is missing, the following rule will be used to calculate LVMi:

$$LVMI = LVM / BSA.$$

Du Bois and Du Bois (1916) will be used to calculate the BSA:

BSA =
$$0.007184 \times W^{0.425} \times H^{0.725}$$
,

where H is the height (cm) measured at screening and W is the weight (kg) measured at the same visit of the cardiac MRI. In case that weight at the visit is missing, the last available weight prior to the visit will be used. This is the formula which is used by the vendor that provides the cardiac MRI assessments.

The analysis will be repeated by gender and by FD classification.

A shift from baseline to Week 52 and to Week 104 in the number of left ventricular fibrosis segments (based on cardiac MRI) will be presented in a shift table by treatment group.

A shift from baseline to Week 52 and to Week 104 in the number of patients who have Hypertrophy at Baseline (Yes / No / Missing) will be presented by treatment group and by treatment group and gender.

For definition of baseline for cardiac MRI, see Section 7.3. For the same reasons discussed in Section 7.3, delays of up to 60 days in the performance of cardiac MRI at Week 52 or Week 104 will be considered with planned visit.

Not all patients can perform cardiac MRI (e.g., patients with pacemaker), and for others only part of the assessments can be done (e.g., patients who cannot receive contrast dye to avoid the contrast nephrotoxicity). This information will be included in the listing.

For some patients, cardiac MRI at Week 104 was postponed due to COVID-19 and eventually performed as part of the extension study, so the data will not be analyzed as part of this study (Section 6).

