14.2.4.1.2	Summary of Plasma Gb3 Concentrations by ADA Status	ITT
14.2.5.1	Summary of Urine Lyso-Gb3 Concentrations	ITT
14.2.5.1.1	Summary of Urine Lyso-Gb3 Concentrations by Gender	ITT
14.2.5.1.2	Summary of Urine Lyso-Gb3 Concentrations by ADA Status	ITT
14.2.6.1	Summary of Cardiac MRI by Hypertrophy Status	ITT
14.2.6.1.1	Summary of Cardiac MRI by Gender and by Hypertrophy Status	ITT
142612	Summary of Cardiac MRI by FD Classification and by	ITT
14.2.6.1.2	Hypertrophy Status	ITT
14.2.6.2	Cardiac MRI - Shift in LVMI Fibrosis Segments	ITT
14.2.6.3	Cardiac MRI – Shift in Hypertrophy Status	ITT
14.2.7	Echocardiogram Qualitative Assessments – Shift from Baseline	ITT
14.2.8.1	Summary of Short Form Brief Pain Inventory - Severity Domains	ITT
142011	Summary of Short Form Brief Pain Inventory - Average Pain	ITT
14.2.8.1.1	Over 24 Hours by Gender	ITT
14.2.8.1.2	Summary of Short Form Brief Pain Inventory - Average Pain	ITT
14.2.0.1.2	Over 24 Hours by ADA Status	111

Г		T
14.2.8.1.3	Summary of Short Form Brief Pain Inventory - Average Pain Over 24 Hours by FD Classification	ITT
14.2.8.2	Short Form Brief Pain Inventory - Proportion of Patients with Improvement or No Change in Average Pain Severity	ITT
14.2.8.3	Summary of Short Form Brief Pain Inventory - Interference Domains	ІТТ
14.2.9.1	Frequency of UPCR Categories	ITT
14.2.9.1.1	Frequency of UPCR Categories by Gender	ITT
14.2.9.1.2	Frequency of UPCR Categories by ADA Status	ITT
14.2.9.1.3	Frequency of UPCR Categories by FD Classification	ITT
14.2.9.1.4	Frequency of UPCR Categories by Usage of ACEi or ARB	ITT
14.2.9.2	UPCR Categories - Shift from Baseline to Week 52 and to Week 104	ITT
14.2.10.1.1	Summary of Stress Test Qualitative Assessments – Overall Impression	ITT
14.2.10.1.2	Summary of Stress Test Qualitative Assessments – Symptoms	ITT
14.2.10.2	Stress Test Overall Impression - Shift from Baseline	ITT
14.2.11.1	Summary of Mainz Severity Score Index (MSSI)	ITT
14.2.11.2	Mainz Severity Score Index (MSSI) Overall Score - Shift from Baseline	ITT
14.2.12.1	Summary of Quality-of-Life EQ-5D-5L Overall Health Score	ITT
14.2.12.2	Frequency of Quality-of-Life EQ-5D-5L Qualitative Assessments	ITT
14.2.12.3	Proportion of Patients with Improvement or No Change of Quality-of-Life EQ-5D-5L Qualitative Assessments	ITT
14.2.13.1	Proportion of Patients Used Pain Medications	ITT
14.2.13.2	Number of Different Pain Medications Used by Patients During the Study	ІТТ

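### The SAP does not clearly plan an all-patient treatment comparison of LVMI change, and its group with missing baseline hypertrophy status can contain no LVMI change

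*SAP*

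**What the plan says.** SAP 2.2.2 lists the secondary endpoints under the line "Change from baseline to all time points in the following measures", and one of them is "Left Ventricular Mass Index (LVMI) (g/m²) by Magnetic Resonance Imaging (MRI". Protocol 8.1 also lists LVMI as a secondary variable. SAP section 10 places all secondary analyses on the ITT set. None of these places mentions hypertrophy.

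SAP 10.4.1 gives the method in this order:

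- LVM, LVMI and ejection fraction are summarised by visit, together with change from baseline.
- A two-sample t interval follows: "A 95% CI for the difference between the two in the change from baseline to Week 52 and to Week 104 arms".
- Then comes the split: "The LVM and LVMI analysis will be done separately for patients who have hypertrophy at baseline", for "patients who don't have this abnormality, and patients whose hypertrophy at baseline is missing".
- The status comes from the index itself: "Hypertrophy is defined as LVMI above 91 g/m² for males and LVMI above 77 g/m² for female".
- A derivation rule follows: "In case that LVM at a visit is available, and LVMi is missing, the following rule will be used to calculate LVMi". It divides LVM by body surface area, using screening height and the weight at the visit or, failing that, the last earlier weight.
- The analysis is then repeated by gender and by FD classification.

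SAP 14.1 lists three cardiac MRI summary tables. Table 14.2.6.1 is titled "Summary of Cardiac MRI by Hypertrophy Status". Tables 14.2.6.1.1 and 14.2.6.1.2 split by hypertrophy status and, in addition, by gender or FD classification. Tables 14.2.6.2 and 14.2.6.3 are shift tables for fibrosis segments and hypertrophy category. SAP 14.2 lists no LVMI figure.

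**The concern.** A named endpoint should have one planned effect estimate in the population for which it is defined. Here the endpoint is stated for everyone, but the analysis text and every listed summary table divide patients by baseline hypertrophy. A programmer working from 10.4.1 and 14.1 could deliver separate stratum intervals and no overall one. In a 2:1 trial of 78 patients those intervals are wide, and a reader who wanted the overall answer would have to combine them after the fact.

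The third stratum is a separate, smaller defect. Patients enter it because the baseline value needed to compute a change is absent, so its rows for LVMI change and for the interval on that change cannot be filled.

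**Working it through.** **No figure to reproduce.** The documents give no SD, effect size or power for LVMI. The check is a reading of the text, followed by an illustration of precision.

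**Step 1: is the split the main layout or an addition?** For gender and FD classification, 10.4.1 says the analysis is repeated, which is the SAP's usual wording for an added breakdown (it also appears in 10.2 and 10.3). For hypertrophy it says the analysis is done separately. The table list points the same way. Plasma Lyso-Gb3 (14.2.3.1), plasma Gb3 (14.2.4.1), urine Lyso-Gb3 (14.2.5.1) and UPCR (14.2.9.1) each have an unsplit parent table with subgroup tables beneath it. Cardiac MRI has no unsplit parent. No pooled or stratum-adjusted LVMI estimate is specified anywhere.

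**Step 2: what can the missing stratum hold?**

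- Hypertrophy status is a function of LVMI and sex only.
- Status at baseline is therefore missing when baseline LVMI is still missing after the LVM/BSA rule has been applied.
- Change in LVMI needs baseline LVMI, so the number of evaluable LVMI changes in this stratum is 0 and no interval for change exists.
- LVMI values at Week 52 or Week 104 can still appear there.
- For LVM, a change is possible only in the narrow case where baseline LVM exists but body surface area cannot be computed.

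**Step 3: precision.** Half-width of the two-sample t 95% CI, in SD units:

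h = t(0.975, n1 + n2 − 2) × √(1/n1 + 1/n2)

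Inputs: 52 and 26 patients by arm (protocol 10.1). The share with hypertrophy is not in the documents, so three splits are assumed. Complete scans, and the same SD overall and within strata, are also assumed.

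| Patients (PRX-102 v agalsidase beta) | t | √(1/n1 + 1/n2) | h (SD) | Ratio to overall |
|---|---|---|---|---|
| All 78 (52 v 26) | 1.992 | 0.240 | 0.48 | 1 |
| 39, each half (26 v 13) | 2.026 | 0.340 | 0.69 | 1.44 |
| 26 (17 v 9) | 2.064 | 0.412 | 0.85 | 1.78 |
| the other 52 (35 v 17) | 2.009 | 0.296 | 0.59 | 1.24 |
| 18 (12 v 6) | 2.120 | 0.500 | 1.06 | 2.22 |
| the other 60 (40 v 20) | 2.002 | 0.274 | 0.55 | 1.15 |

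With the planned 44 and 22 completers (protocol 10.1) the overall half-width is 1.998 × 0.261 = 0.52 SD. At a 50% split each stratum (22 v 11) has 2.040 × 0.369 = 0.75 SD, again 1.44 times as wide.

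**The case against.** The strongest reply is that an overall comparison may already be intended. The interval sentence in 10.4.1 comes before the split and names no stratum, section 10 puts secondary analyses on the ITT set, and nothing says an overall interval is dropped. The table titles are weak evidence of absence:

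- The split covers LVM and LVMI only, yet ejection fraction has no listed home except these same tables, so a title ending in hypertrophy status need not exclude unsplit content.
- The list is incomplete elsewhere. Section 9.3 calls for its analyses on ITT and PP, but the MMRM table 14.2.1.8 is ITT only. Section 10.4.1 asks for the hypertrophy shift by gender, but only one table, 14.2.6.3, is listed.
- The shells are a separate document, and a total column in 14.2.6.1 cannot be excluded.

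All of this stands. A reader might infer that the SAP rules out an all-patient estimate. The documents do not support that; they support only that none is clearly planned. The text still needs to say which is meant.

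A reader might also infer that the missing stratum is empty. It is not: post-baseline values belong there, and only the change rows are blank. Blank rows bias nothing.

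On size, quoting only the smaller stratum would overstate the loss, so the table above gives both. Scans lost to pacemakers or COVID-19 delay would reduce an overall analysis too, and are not a cost of the split. Two stratum estimates could also be combined by inverse variance, and the cardiac MRI data are listed (Listing 16.2.2.3). These are workarounds, not a planned estimate.

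**Conclusion.** The point holds as a gap in specification. For LVMI change, the text and table list lead to stratum-specific comparisons and do not clearly provide an all-patient one. The missing stratum cannot contribute to the endpoint as defined.

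The cost in precision depends on a hypertrophy share that the documents do not give. It runs from little in a large stratum to more than double the interval width in a stratum of 18, and it rests on complete scans and equal SDs.

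A reader might go further and say that the trial cannot answer its cardiac question. That is too strong. The documents state no cardiac hypothesis, margin or power, and SAP 7.6.2 makes no significance claims for secondary endpoints. Nor is any weight placed on where LVMI falls in the list: the protocol and SAP order the endpoints differently, and neither calls the order a ranking. The severity is modest. The change is worth making because it uses data already collected and gives the endpoint one interpretable estimate.

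**What to change.** In SAP 10.4.1, add one between-arm analysis of LVMI change from baseline to Week 52 and to Week 104, in all ITT patients with a baseline scan and a scan at the relevant visit. Report the difference and its 95% CI, and list an unsplit table for it in 14.1. Adjust for baseline LVMI, as section 10.2 already does for log plasma Lyso-Gb3 at baseline. Adding sex is optional. The adjustment is an improvement in precision, not the correction of an error, since the SAP uses unadjusted two-sample t intervals for several other secondary endpoints.

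Keep the hypertrophy yes and no tables, labelled as subgroups. For change from baseline, show the missing group only as a count or in the listing. If a total column in Table 14.2.6.1 was always intended, say so in 10.4.1 and in the table title.

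The cost is one table and a few lines of code, with no new data.
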